APPENDIX VII-B: MEDICATION DIARY (LAROTRECTINIB LIQUID FORMULATION)

COG Patient ID: _____ ACC # : _____ Institution : _____ BSA: _____ m²
Please do not write patient names on this form.

Instructions: Store the larotrectinib liquid formulation in the refrigerator.

Complete each day with the time and dose given for larotrectinib. If a dose is accidentally skipped, leave that section blank. **Make note of other drugs and supplements taken in the Comments section below.** You should take each dose of larotrectinib approximately 12 hours apart, at about the same time each day. If you vomit after taking a dose, DO NOT retake the dose. This should be noted in the comments section. If you forget a dose and remember it within 4 hours of the time the dose was due, you should take the dose at that time. Otherwise, you should skip the forgotten dose. Either way, the next dose should be taken at the usual time. If a dose is accidentally skipped leave that section blank. Add the dates to the calendar below and return the completed diary and the empty liquid formulation bottle(s) or any leftover liquid formulation to the study clinic at each visit (weekly during Cycle 1, and then after each treatment cycle).

| EXAMPLE | | | | | |
|---------|----------|------|---|------------------------|---|
| Day | Date | Time | AM Dose: Take _____ mL | PM Dose: Take _____ mL | Comments (Describe any missed or extra doses, vomiting and/or bothersome effects.) |
| | | | Amount of larotrectinib liquid formulation taken (mL) | | |
| Day 1 | 09/20/18 | 8:30 | AM | 2 | He felt nauseated an hour after taking the drug but did not vomit. |
| | | 8:30 | PM | 2 | |

| Cycle #: _____ Start Date: _____ / _____ / _____ End Date: _____ / _____ / _____ | | | | | | Dose Level: _____ mg/m ² /dose |
|---|------|------|---|------------------------|---|---|
| Day | Date | Time | AM Dose: Take _____ mL | PM Dose: Take _____ mL | Comments (Describe any missed or extra doses, vomiting and/or bothersome effects.) | |
| | | | Amount of larotrectinib liquid formulation taken (mL) | | | |
| Day 1 | | AM | | | | |
| | | PM | | | | |
| Day 2 | | AM | | | | |
| | | PM | | | | |
| Day 3 | | AM | | | | |
| | | PM | | | | |
| Day 4 | | AM | | | | |
| | | PM | | | | |
| Day 5 | | AM | | | | |
| | | PM | | | | |
| Day 6 | | AM | | | | |
| | | PM | | | | |
| Day 7 | | AM | | | | |
| | | PM | | | | |
| Day 8 | | AM | | | | |
| | | PM | | | | |

| | | | | |
|---------------|--|-----------|--|--|
| Day 9 | | AM | | |
| | | PM | | |
| Day 10 | | AM | | |
| | | PM | | |
| Day 11 | | AM | | |
| | | PM | | |
| Day 12 | | AM | | |
| | | PM | | |
| Day 13 | | AM | | |
| | | PM | | |
| Day 14 | | AM | | |
| | | PM | | |
| Day 15 | | AM | | |
| | | PM | | |
| Day 16 | | AM | | |
| | | PM | | |
| Day 17 | | AM | | |
| | | PM | | |
| Day 18 | | AM | | |
| | | PM | | |
| Day 19 | | AM | | |
| | | PM | | |
| Day 20 | | AM | | |
| | | PM | | |
| Day 21 | | AM | | |
| | | PM | | |
| Day 22 | | AM | | |
| | | PM | | |
| Day 23 | | AM | | |
| | | PM | | |
| Day 24 | | AM | | |
| | | PM | | |
| Day 25 | | AM | | |
| | | PM | | |
| Day 26 | | AM | | |
| | | PM | | |
| Day 27 | | AM | | |
| | | PM | | |
| Day 28 | | AM | | |
| | | PM | | |

[figure not shown]
Instructions for drawing up larotrectinib oral solution into a syringe:
Information and images adapted from VITRAKVI® (larotrectinib) package insert.⁵³

Important information about measuring larotrectinib oral solution:

- Always use the oral syringes provided with larotrectinib to make sure that you correctly measure the prescribed dose.
- When you receive larotrectinib oral solution, you will get 1 or more glass bottles of larotrectinib oral solution and a bottle adapter.
- You will receive oral syringes that are marked to help you correctly measure the prescribed dose of larotrectinib oral solution. Each oral syringe may be used for up to a 7-day period and then must be discarded. Do not use a household teaspoon to measure the dose.

Supplies needed for administering larotrectinib (See Figure A):

- Bottle of larotrectinib
- Oral syringe
- Bottle adapter
- Gloves

Figure A

[figure not shown]
Step 1: Put on gloves. Place the larotrectinib bottle on a flat work surface. Open the bottle by pushing down firmly on the child-resistant cap and turning it in the direction of the arrow (counter-clockwise). See Figure B. Do not throw away the child-resistant cap.

Figure B

[figure not shown]

Step 2: Insert the bottle adapter by pressing it into the bottle neck and make sure it is secure. See Figure C. Do not remove the bottle adapter. If the bottle adapter is missing, talk to your healthcare provider.

[figure not shown]
Figure C

Step 3: Remove the oral syringe from the wrapper. Throw the wrapper away in your household trash. The barrel of the oral syringe has markings in milliliters (mL). Look at the markings on the barrel of the oral syringe and find the mL marking that matches the larotrectinib oral solution dose in mL prescribed by your healthcare provider. See Figure D.

[figure not shown]
Figure D

Step 4: With the bottle on your flat work surface, use 1 hand to hold the bottle upright. Using your other hand, push the air out of the oral syringe by pushing the plunger down. Then, insert the tip of the oral syringe into the bottle adapter at the top of the bottle. See Figure E. The tip of the oral syringe should fit snugly into the hole of the bottle adapter.

Figure E

[figure not shown]
Step 5: Use 1 hand to hold the oral syringe in place. With the other hand, turn the bottle upside down. Pull back on the plunger until the top of the plunger lines up with the marking on the barrel of the oral syringe that matches the dose of larotrectinib oral solution prescribed by your healthcare provider. See Figure F. Your dose may be different than the dose shown in Figure F.

Figure F

[figure not shown]
Step 6: Check for air bubbles in the oral syringe. If you see air bubbles, push up gently on the plunger to push any large air bubbles back into the bottle. Then, pull back on the plunger to the prescribed dose. See Figure G.

Figure G

Step 7: Turn the bottle upright again and place it on your work surface. Remove the oral syringe from the bottle adapter by gently pulling up on the syringe barrel. See Figure H. Do not push on the plunger during this step. The bottle adapter should stay attached to the bottle.

Figure H

[figure not shown]
Step 8: Place the tip of the oral syringe into the child's mouth against the inside of the cheek. Slowly squirt larotrectinib oral solution into the mouth by pressing down on the plunger and allow the child to swallow. See Figure I. If the child has an NG or G-tube you may administer larotrectinib via the tube instead of into the mouth if instructed by your healthcare provider. The child should be kept in an upright position for a few minutes right after giving a dose of larotrectinib.

Figure I

Step 9: Replace the child-resistant cap on the bottle of larotrectinib oral solution. Do not remove the bottle adapter. Close the bottle by turning the bottle cap in the direction of the arrow (clockwise). See Figure J.

Figure J

[figure not shown]

Cleaning instructions for oral syringe:

Follow the instructions below for cleaning the oral syringe (Step 10 through Step 16). After 7 days of use, throw away the oral syringe in your household trash. Use a new one for the next 7 days.

[figure not shown]
Step 10: Remove plunger from the barrel of the oral syringe. See Figure K.

Figure K

[figure not shown]
Step 11: Rinse the barrel and plunger in warm running water to help ensure that all of the medicine has been removed from the oral syringe. See Figure L. Do not boil the oral syringe.

Figure L

[figure not shown]
Step 12: Re-insert the plunger into the barrel of the oral syringe. See Figure M.

Figure M

[figure not shown]
Step 13: Draw warm water several times into the oral syringe and squirt out again until all of the medicine has been removed from the oral syringe. See Figure N.

Figure N

Step 14: Disassemble the oral syringe, and rinse the barrel and plunger again with warm water. See Figure O.

Figure O

Step 15: Shake off excess water or wipe off the outside, and the place the barrel and plunger on a clean, dry paper towel to dry. See Figure P. Remove gloves and place in regular household trash.

Figure P

Step 16: Assemble the oral syringe and store in a clean place until the next use.
Replace the oral syringe after 7 days of use, or if:

- there is any damage to the barrel, plunger, or tip
- the dosage marking is no longer clearly recognizable
- it becomes difficult to move the plunger

APPENDIX VIII: CSF AND PLASMA PHARMACOKINETIC STUDY FORM

COG Pt ID # _____

Date: _____

Please do not write patient names on this form or on samples.

Patient Weight: _____ kg

Body Surface Area: _____ m²Larotrectinib Dose Level: _____ mg/m² BID

Larotrectinib Daily Dose: _____ mg BID

For all patients with leukemia, a CSF and plasma sample will be collected after Cycle 1, during the first disease evaluation after starting protocol therapy. The plasma sample will be obtained as close as possible to the same time as the CSF sample. In patients who are undergoing lumbar puncture (LP) for intrathecal chemotherapy administration, a CSF and plasma sample will also be collected at the time of lumbar puncture. The plasma sample will be obtained as close as possible to the same time as the CSF sample. Samples will be collected during Cycle 1 on the following days: Day 8, Day 15, and Day 22. There is no required time window from the most recent larotrectinib dose, but the dose and time of administration must be recorded.

Record the exact time both samples are drawn along with the exact time and dose of the most recent dose of larotrectinib that was given prior to the lumbar puncture.

| Sample No. | Time Point | Scheduled Collection Time | Actual Date Sample Collected | Actual Time CSF Collected (24-hr clock) | Actual Time Plasma Collected (24-hr clock) |
|--|-----------------|----------------------------|------------------------------|---|--|
| Most recent larotrectinib dose prior to LP | | | Date: _____ | Time Dose Given: : | |
| Actual larotrectinib dose administered _____ mg = _____ mg/m ² | | | | | |
| 1* | Cycle 1, Day 8 | At time of lumbar puncture | | : | : |
| Most recent larotrectinib dose prior to LP | | | Date: _____ | Time Dose Given: : | |
| Actual larotrectinib dose administered _____ mg = _____ mg/m ² | | | | | |
| 2* | Cycle 1, Day 15 | At time of lumbar puncture | | : | : |
| Most recent larotrectinib dose prior to LP | | | Date: _____ | Time Dose Given: : | |
| Actual larotrectinib dose administered _____ mg = _____ mg/m ² | | | | | |
| 3* | Cycle 1, Day 22 | At time of lumbar puncture | | : | : |
| Most recent larotrectinib dose prior to LP | | | Date: _____ | Time Dose Given: : | |
| Actual larotrectinib dose administered _____ mg = _____ mg/m ² | | | | | |
| 4 | End of Cycle 1 | At time of lumbar puncture | | : | : |

* Only for leukemia patients receiving intrathecal therapy.

One copy of this CSF and Plasma Pharmacokinetic Study Form should be uploaded into RAVE. A second copy should be sent with the samples to the address listed in [Section 7.3.3.4](#). See [Section 7.3.3.3](#) for detailed guidelines for packaging and shipping CSF and plasma PK samples.

Notes _____

If this form will be used as a source document, the site personnel who collected the samples must sign and date this form below:

Signature: _____ Date: _____
(site personnel responsible for collection of samples)

APPENDIX IX: PERFORMANCE STATUS SCALES/SCORES

| Karnofsky | | Lansky | |
|-----------|--|--------|--|
| Score | Description | Score | Description |
| 100 | Normal, no complaints, no evidence of disease | 100 | Fully active, normal. |
| 90 | Able to carry on normal activity, minor signs or symptoms of disease. | 90 | Minor restrictions in physically strenuous activity. |
| 80 | Normal activity with effort; some signs or symptoms of disease. | 80 | Active, but tires more quickly |
| 70 | Cares for self, unable to carry on normal activity or do active work. | 70 | Both greater restriction of and less time spent in play activity. |
| 60 | Required occasional assistance, but is able to care for most of his/her needs. | 60 | Up and around, but minimal active play; keeps busy with quieter activities. |
| 50 | Requires considerable assistance and frequent medical care. | 50 | Gets dressed, but lies around much of the day; no active play, able to participate in all quiet play and activities. |
| 40 | Disabled, requires special care and assistance. | 40 | Mostly in bed; participates in quiet activities. |
| 30 | Severely disabled, hospitalization indicated. Death not imminent. | 30 | In bed; needs assistance even for quiet play. |
| 20 | Very sick, hospitalization indicated. Death not imminent. | 20 | Often sleeping; play entirely limited to very passive activities. |
| 10 | Moribund, fatal processes progressing rapidly. | 10 | No play; does not get out of bed. |

APPENDIX X-A: Larotrectinib Dosing Nomogram (CAPSULE formulation)

Drug doses should be adjusted based on the BSA calculated from height and weight measured within 7 days prior to the beginning of each cycle.

Patients with a BSA $\geq 0.66 \text{ m}^2$ may take either the capsule or liquid formulation. Patients $< 0.66 \text{ m}^2$ must receive the liquid formulation (See [Appendix X-B](#) for dosing preparation of the larotrectinib liquid formulation.

Larotrectinib Dosing Table

| BSA (m ²) | Starting Dose 100 mg/m ² / dose PO BID | Dose Reduction 1 | Dose Reduction 2 | Dose Reduction 3 |
|-----------------------|---|------------------|--|--|
| 0.66-0.87 | 75 mg BID | 50 mg BID | 34 mg/dose BID Use liquid formulation | 18 mg/dose BID Use liquid formulation |
| ≥ 0.88 | 100 mg BID | 75 mg BID | 50 mg BID | 25 mg BID |

Patients with BSA $\geq 0.66 \text{ m}^2$ may be switched to the liquid formulation at the same dose level if their ability to swallow capsules changes during the treatment.

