4.1.1 Dose Reduction

Up to three dose reductions of larotrectinib will be allowed for dose limiting toxicities as outlined in [Section 5.0](#) for patients who recover and meet starting criteria as outlined in [Section 3.2.6](#) within 21 days following drug discontinuation:

- 1st dose reduction: 75 mg/m²/dose BID (maximum of 75 mg/dose BID)
- 2nd dose reduction: 50 mg/m²/dose BID (maximum of 50 mg/dose BID)
- 3rd dose reduction: 25 mg/m²/dose BID (maximum of 25 mg/dose BID)

Patients who do not recover to meet starting criteria within 21 days will be removed from protocol therapy. Patients who experience DLT as outlined in [Section 5.0](#) after three dose reductions will be removed from protocol therapy.

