4.1.2 Dose Escalation

There will be no drug dose escalation except for those based on growth of the patient to maintain the same dose on a mg/m² basis. The dose of larotrectinib should be recalculated at the start of each cycle based on a recent (within 7 days) height and weight.

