5.2 Dose Modifications for Hematological Toxicity

- 5.2.1 If a patient experiences hematological dose limiting toxicity as defined in [Section 5.1.2](#), the treatment will be held. Counts should be checked every 3-4 days during this time. If the toxicity resolves to meet eligibility parameters within 21 days of drug discontinuation, the patient may resume treatment with a dose reduction. The first dose reduction will be to 75 mg/m²/dose BID (cap of 75 mg/dose BID), the second dose reduction will be to 50 mg/m²/dose BID (cap of 50 mg/dose BID), and a third dose reduction of 25 mg/m²/dose BID (cap of 25 mg/dose BID). Doses reduced for toxicity will not be re-escalated, even if there is minimal or no toxicity with the reduced dose, except as required due to patient growth to maintain the same BSA-based dose.
- 5.2.2 If toxicity does not resolve to meet eligibility parameters within 21 days of drug discontinuation, the patient must be removed from protocol therapy.
- 5.2.3 Up to 3 dose reductions are permitted per patient. If hematological dose-limiting toxicity recurs in a patient who has resumed treatment following three dose reductions, the patient must be removed from protocol therapy.

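### In Appendix X-A, a capsule patient cut to 50 mg BID after a DLT is read back to 75 mg BID once BSA reaches 0.88 m², a rise in delivered mg/m² far beyond what growth accounts for

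*Combined protocol and SAP*

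**What the plan says.** Appendix X-A has two BSA bands. The lower reads "0.66-0.87 | 75 mg BID | 50 mg BID", followed by 34 mg and 18 mg BID at Dose Reductions 2 and 3, both marked for the liquid formulation. The row for 0.88 m² and above reads "100 mg BID | 75 mg BID | 50 mg BID | 25 mg BID".

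Section 4.1.1 defines the first reduced level as "1st dose reduction: 75 mg/m²/dose BID (maximum of 75 mg/dose BID"). Section 4.1.2 makes the dose follow growth: "The dose of larotrectinib should be recalculated at the start of each cycle based on a recent (within 7 days) height and weight". It rules out other escalation, "except for those based on growth of the patient to maintain the same dose on a mg/m² basis".

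Section 5.2.1 states "Doses reduced for toxicity will not be re-escalated, even if there is minimal or no toxicity with the reduced dose", and the same sentence continues "except as required due to patient growth to maintain the same BSA-based dose". Section 5.3.1 repeats the rule and the exception for non-hematological toxicity.

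The treatment details (for example Sections 4.2.3 and 4.3.3) have capsule doses rounded to the nearest multiple of 25 mg. Appendix X-B doses the liquid by formula, at 20 mg/mL, in steps of 0.1 mL up to 45 mg and 0.2 mL above that.

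**The concern.** The table and the text pull apart at the band boundary. A patient on capsules at Dose Reduction 1 with BSA 0.87 m² takes 50 mg BID. At the next cycle, with BSA 0.88 m², the same column gives 75 mg BID. That is the lower band's starting dose, and so the milligram dose on which this patient had the DLT. The growth exception is worded as preserving a BSA-based dose, and a 50% rise in milligrams for roughly 1% growth is hard to fit under it. No footnote covers the crossing.

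At stake is the safety of a small number of children. A site that follows the table exactly can return a patient to the milligram dose that was not tolerated. A recurrent DLT would then use another of the three permitted reductions.

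**Working it through.** **Inputs.** Table cells from Appendix X-A; level definitions and caps from Section 4.1.1; growth exceptions from 4.1.2, 5.2.1 and 5.3.1; nearest-25-mg rounding from 4.3.3; liquid formula and rounding from Appendix X-B.

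**1. Does the table follow from the rules?** Capsule dose = min(level × BSA, cap), rounded to the nearest 25 mg.
- Starting level: 100 × 0.66 = 66 → 75; 100 × 0.87 = 87 → 75; 100 × 0.88 = 88 → 100. The column reproduces at every BSA from 0.66 m² up.
- Dose Reduction 1: 75 × 0.66 = 49.5 → 50; 75 × 0.83 = 62.25 → 50; 75 × 0.88 = 66 → 75. These agree with the table.
- At 0.84–0.87 m² the column does not reproduce: 75 × 0.84 = 63.0 and 75 × 0.87 = 65.25 both round to 75, while the table says 50.

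**2. Size of the step.** Delivered dose = table mg ÷ BSA. BSA growth is 0.88 / 0.87 − 1 = 1.15%.

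| Level | mg at 0.87 → 0.88 m² | mg/m² at 0.87 → 0.88 m² | Change in mg | Change in mg/m² |
|---|---|---|---|---|
| Start | 75 → 100 | 86.2 → 113.6 | +33% | +32% |
| Reduction 1 | 50 → 75 | 57.5 → 85.2 | +50% | +48% |

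Against the nominal 75 mg/m², Reduction 1 delivers 57.5 / 75 = 77% at 0.87 m² and 85.2 / 75 = 114% at 0.88 m². As a yardstick only, not a proposed dose: holding 57.5 mg/m² constant changes 50 mg to 50 × 0.88 / 0.87 = 50.6 mg.

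**3. Comparison with the dose at the DLT.** The milligrams are equal (75 and 75). In mg/m², 85.2 compares with 75 ÷ BSA at the DLT:

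| BSA at DLT (m²) | mg/m² at DLT | 85.2 mg/m² is lower by |
|---|---|---|
| 0.87 | 86.2 | 1% |
| 0.82 | 91.5 | 7% |
| 0.76 | 98.7 | 14% |
| 0.66 | 113.6 | 25% |

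**4. The same crossing on liquid.** Reduction 1 under Appendix X-B: 75 × 0.87 / 20 = 3.26 mL → 3.2 mL = 64 mg; 75 × 0.88 / 20 = 3.30 mL, a rounding tie between 3.2 and 3.4 mL, so 64 or 68 mg. The change is at most 4 / 64 = 6%.

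**5. Reductions 2 and 3.** The lower-band cells (34 and 18 mg) are liquid.
- If the patient is read from the capsule row at 0.88 m², the dose becomes 50 and 25 mg, or 39.1 → 56.8 mg/m² (+45%) and 20.7 → 28.4 mg/m² (+37%).
- If Appendix X-B governs on both sides, Reduction 2 is 43.5 → 44 mg at 0.87 m² and 44 mg at 0.88 m². Reduction 3 is 21.75 → 22 mg and then 22 mg. There is no step.
- At 0.87 m² the two appendices give different liquid doses (34 against 44 mg; 18 against 22 mg), so which one applies matters.

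**6. Who could cross.** The documents give no growth rate. Assuming 0.03–0.06 m² per year, 26 cycles (26 × 28 = 728 days, about 2 years) add 0.06–0.12 m². A child would then need to start at or above about 0.82 m² (slower growth) or 0.76 m² (faster growth).

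**The case against.** The strongest reply is that the reduction levels are nominal. Reduction 1 is 75 mg/m² capped at 75 mg, and a patient who grows past 0.88 m² is still on it. Growth is an explicit exception, and Section 4.1 sends sites to the nomogram. Coarse steps come with 25 mg rounding: the starting column also jumps by 32% in mg/m² at the same boundary, so a strict delivered-dose reading would fault the whole table. The upper Reduction 1 cell does follow the rounding rule. The lower cell departs from it at 0.84–0.87 m², where strict rounding would make Reduction 1 equal the 75 mg starting dose, so the departure preserves a real cut in milligrams.

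Most of this stands. It shows that no breach occurs if the sponsor means the nominal level. It does not settle which meaning applies, since 4.1.2 says only that the mg/m² dose is to be kept. It also leaves a patient with a DLT returning to the same milligram dose, and a table cell that disagrees with the stated rounding.

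A reader might infer three stronger things that the documents do not support:
- That re-escalation is banned outright and the table breaks the ban. The sentence carries a growth exception.
- That the dose reduction is wholly undone. That holds in milligrams; in mg/m² it is nearly so only when the DLT occurred close to 0.87 m².
- That the toxicity analysis is blurred by dose level. Aim 1.2.3 is descriptive, and Section 9.3 tabulates toxicity by type and grade, not by dose level.

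**Conclusion.** The point holds in limited form. Appendix X-A, followed literally with per-cycle BSA, moves a capsule patient at Dose Reduction 1 from 50 to 75 mg BID between 0.87 and 0.88 m². Delivered dose rises by 48% for about 1% growth. This goes beyond the growth exception if that exception refers to delivered mg/m²; it does not if it refers to the nominal level. The text should say which. The disagreement between the lower cell and the rounding rule at 0.84–0.87 m² holds on either reading. A step at Reductions 2 and 3 is not established: the jump to 50 or 25 mg requires reading the capsule row, and nothing in the documents requires a return to capsules.

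Few patients can be affected. It takes capsules, BSA of 0.66–0.87 m², a DLT on 75 mg, and later growth past the cut. Section 2.7.1 reports that accrual is complete and that median age at enrollment was 8 months; the documents do not say whether anyone is still on treatment. After a recurrent DLT in the Reduction 1 case, further reductions remain, and removal for recurrence applies only after three. No endpoint, alpha or power depends on this. It is a safety-related inconsistency worth correcting, with no effect on inference.

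**What to change.** Reconcile Appendix X-A with Sections 4.1.2, 5.2.1 and 5.3.1, the capsule rounding rule in the treatment details, and Appendix X-B. In particular:
- Add a footnote to Appendix X-A stating how a patient on a reduced level whose BSA crosses 0.88 m² is handled.
- State whether keeping the same BSA-based dose refers to the nominal level or to the delivered mg/m².
- Either note that the lower-band Reduction 1 cell is an intended exception to rounding at 0.84–0.87 m², or bring the cell and the rule into agreement.
- State which appendix governs a patient at Reduction 2 or 3 who is on liquid.

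Which dose applies is for the sponsor's clinical team; none is proposed here. The cost is a footnote and a few words of cross-reference in an amendment, with no new data and no extra patients.
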